5.13. Subject Lost to Follow Up

Due to the observational nature of this Registry and the variability of real - world follow-up frequency, patients will be declared lost to follow-up according to site's standard modalities or at the end of the 5 years FU windows. Attempt to contact the subject or next of kin will be documented in the subject files.

5.14. Subject Registry Completion

A subject has completed the registry when he/she has reached the 5 years post treatment (+/- 1 month) and the visit has been properly recorded in the EDC. Any subject who does not complete these requirements due to voluntary withdrawal, physician withdrawal, death, or any other reason will be considered a withdrawal.

After subject registry completion the site standard of care will be continued.

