3.2. Description of Registry Design

This multicenter, single-arm retrospective and prospective registry is being conducted to confirm the clinical performance and safety of [REDACTED] when used as a Bridging Stent with Branched and Fenestrated Endografts in the Treatment of Aortic Aneurysms Involving the Renal-Mesenteric Arteries.

A single arm design was chosen as the clinical application does not readily lend to randomization due to involvement of multiple vessels and variability with respect to the main body design.

A retrospective and prospective registry was determined to be suitable observational study design to reliably answer the research question, based on consistency of device design, procedures, clinical results available and operative techniques.

Up to 15 sites in Europe will be required to enroll a minimum of 220 patients that have had treatment with [REDACTED] when used as a Bridging Stent with Branched and Fenestrated Endografts in the Treatment of Aortic Aneurysms Involving the Renal-Mesenteric Arteries.

Each site cannot contribute to more than 10% of the total patient for each cohort without sponsor approval, with a maximum of 30% of total enrollment for a single site. See section 4.1 for more details.

The Sponsor or designee will maintain an updated list of all principal investigators, site names, and addresses. This list shall be kept separately from this protocol.

Subjects may be enrolled when all inclusion and no exclusion criteria are met as specified in section 4.2. Patients are enrolled into the registry when they provide consent or consent is waived and meet all inclusion and exclusion criteria.

Subjects' medical records will be reviewed by the investigator and specific data will be collected retrospectively and prospectively for up to 5 years of follow-up from the index procedure.

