5.11. Follow Up

All follow-up performed from the index procedure to the ICF signature will be collected retrospectively. FU data will be collected from the information already present in the medical chart.

From the date of the enrollment, all FU visits including any imaging, performed according to hospital standard of care, will be collected up to 5 years post index procedure.

In addition to in person visits, remote phone follow-up is also acceptable and clinical information obtained via phone can be collected.

For testing done at institutions different than the registry site, or in case no follow-up data are available, investigators should make any efforts to retrieve documentation from the patient or from other records/sources (e.g. hospital databases, family doctor, family members).

Subjects will continue to be followed by the site's standard of care after completion of the registry.

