10.4. Data Analysis

10.4.1. Timing of Analyses

The analysis to test the primary hypothesis will be conducted once all subjects have completed their 12 Month follow-up, data has been entered and cleaned in the EDC system. Subjects with a visit within 90 days of the annual time frames will be considered for analysis of the annual outcomes. [REDACTED]

[REDACTED]. The subject follow-up will continue for five years, and the final analysis will be done once all subjects have completed five-year follow-up. Separate analysis will be performed for FEVAR and BEVAR cohorts. No interim analysis for the early termination of registry is planned due to the post marketing usage of the [REDACTED] and retrospective nature of the enrollment. In addition, once the primary analysis has been performed and hypothesis tested, further analyses may also be performed as needed for annual reports, presentations and publications based on interim data or at any other time at the discretion of Gore.

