5.0 Statistical Analyses

[figure not shown]
Analysis Populations

- The registry population will consist of patients that have had treatment with GORE® [REDACTED]® [REDACTED] and that meet the registry eligibility criteria.

CONFIDENTIAL INFORMATION

Page 10 of 15

Timing of Analyses

The analysis to test the primary hypothesis will be conducted once all subjects have completed their 12 Month follow-up, data has been entered and cleaned in the EDC system. Subjects with a visit within 90 days of the annual time frames (i.e., 275 – 455 for 12 Month visit) would be considered for analysis of the annual outcomes. In case of the multiple visits within the interval, the visit closest to and preceding the annual time point would be considered for the determination of the outcomes.

[REDACTED]
The subject follow-up will continue for five years, and the final analysis will be done once all subjects have completed five-year follow-up. [REDACTED]

[REDACTED] No interim analysis for the early termination of registry is planned due to the post marketing usage of the [REDACTED] Stent Graft and retrospective nature of the enrollment. In addition, once the primary analysis has been performed and hypothesis tested, further analyses may also be performed as needed for annual reports, presentations and publications based on interim data or at any other time at the discretion of Gore.

CONFIDENTIAL INFORMATION

Page 11 of 15

Analysis Populations

Intent-to-Treat (ITT) dataset will consist of all enrolled patients meeting the inclusion / exclusion criteria and treated at least one vessel with the [REDACTED] Stent Graft. A subset of the ITT dataset will be further identified of subjects with all vessels treated with [REDACTED] and another subset with all vessels treated with [REDACTED] only. ITT dataset will be used for the analysis of the primary and secondary endpoints. Similarly, per vessel analysis will be performed with all three datasets after identifying each vessel treated by [REDACTED] and also of the vessels treated without [REDACTED]

[REDACTED]

Pooling of Data

All sites in the registry will follow a common protocol and the data will be monitored to assure compliance. The data collection and handling procedures will be the same at all registry Sites. As such, there is no concern in pooling data from different sites together for analysis.

[REDACTED]

Statistical Analysis of Primary Endpoint(s)

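### The year-5 rules for collection, completion and analysis do not agree: read literally, 33% to 50% of the calendar days in the 5-year analysis window fall after data collection stops

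*Protocol*

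**What the plan says.** Five places bear on when year 5 ends.

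- **Collection.** Protocol 3.2 says that "specific data will be collected retrospectively and prospectively for up to 5 years of follow-up from the index procedure". Protocol 5.11 says that visits and imaging after enrolment "will be collected up to 5 years post index procedure". Neither gives an allowance after the anniversary.
- **Completion.** Under Protocol 5.14 a subject has completed when he or she "has reached the 5 years post treatment (+/- 1 month", and the visit must also be entered in the data capture system. A subject who falls short "due to voluntary withdrawal, physician withdrawal, death, or any other reason will be considered a withdrawal".
- **Loss to follow-up.** Protocol 5.13 refers to the end of a 5-year follow-up window but does not define it.
- **Adverse events.** Protocol 9.1.3 ends reporting at the 5-year visit, not on a stated day.
- **Analysis.** Protocol 10.4.1 has "Subjects with a visit within 90 days of the annual time frames will be considered for analysis of the annual outcomes". SAP 5.0 repeats the rule with a worked example: "Subjects with a visit within 90 days of the annual time frames (i.e., 275 – 455 for 12 Month visit". Neither makes an exception for year 5. Where a subject has several visits in the interval, the SAP says that "the visit closest to and preceding the annual time point would be considered for the determination of the outcomes".

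The Protocol Modification Summary records that version 2 added the visit windows to 10.4.1. It lists no matching change to 5.11 or 5.14.

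**The concern.** The registry schedules no visits of its own. Follow-up is set by local practice (Protocol section 5 introduction, 5.9, 5.11), so some year-5 scans can be expected after the anniversary. A routine scan at 5 years plus 2 months is valid for the analysis, yet on the literal text it lies outside both collection and completion.

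No imputation is planned (Protocol 10.4.5, 10.4.6), and SAP 4.0 analyses the data available. A subject whose only in-window scan comes after the stop would therefore drop out of the 5-year imaging result. At years 1 to 4 collection continues past the anniversary, so this cut-off does not arise there.

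The completion rule adds a second problem. On one reading, a subject can be analysed at 5 years and also be counted as a withdrawal, so the disposition and analysis counts would not tally. The final analysis waits until all subjects have completed 5-year follow-up (Protocol 10.4.1), so the meaning of completion also affects its timing. Because the last day is not stated once, sites may apply different cut-offs.

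**Working it through.** **Inputs from the documents:** analysis window of 90 days either side of the anniversary (Protocol 10.4.1, SAP 5.0); collection up to 5 years (Protocol 3.2, 5.11); completion at 5 years plus or minus 1 month (Protocol 5.14).

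**Assumptions:** 5 years = 5 × 365.25 = 1826.25, taken as day 1826 (day 1825 also tried); 1 month = 30 days (28 and 31 also tried).

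**1. Reproduce the SAP's own window.** At 12 months, 365 − 90 = 275 and 365 + 90 = 455. This matches the SAP, so the rule is a full 90 days on each side.

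**2. Apply the rule at year 5.** 1826 − 90 = 1736 and 1826 + 90 = 1916. The window holds 1916 − 1736 + 1 = 181 days.

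**3. Days after the collection stop.**

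| Collection stops at | In-window days after the stop | Share of 181 |
|---|---|---|
| exactly 5 years (day 1826) | 1916 − 1826 = 90 | 49.7% |
| 5 years + 30 days (day 1856) | 1916 − 1856 = 60 | 33.1% |

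With a 28-day month the second row is 62/181 = 34.3%; with a 31-day month it is 59/181 = 32.6%. Starting from day 1825 leaves every count unchanged.

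**4. Days outside the completion window.** That window opens on day 1826 − 30 = 1796. Days 1736 to 1795 (60 days) come before it and days 1857 to 1916 (60 days) come after it. Together they make 120/181 = 66.3% of the analysis window.

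**5. Two example subjects, each with a single visit in the window.**

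- Scan at 5 years + 60 days (day 1886): inside the analysis window, after the literal collection stop, and outside the completion window.
- Scan at 5 years − 60 days (day 1766): collected and analysed at 5 years. It is more than one month early, so if 5.14 applies the month to the visit date, this subject is also a withdrawal.

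These are fractions of calendar days. Turning them into fractions of subjects would need the distribution of visit dates, which the documents do not give.

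**The case against.** The strongest reply is that the documents do not fix a hard stop on the anniversary. Section 5.14 allows a month, 5.13 implies that some window exists, and 9.1.3 follows the visit and not the calendar. The sentence in 5.11 on the retrospective phase carries no 5-year cap, although 3.2 applies the limit to both phases. This stands: the true stop is unclear. It removes the claim that the late part of the window cannot hold data, but it leaves the inconsistency.

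Other limits also stand.

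- In 5.14 the month may qualify reaching 5 years and not the date of the visit. A subject seen on day 1766 who then reaches 5 years could be read as complete.
- The withdrawal label deletes nothing. Protocol 5.12 keeps data collected before withdrawal, and the analysis selects by visit date and not by completion status. The label itself affects disposition counts.
- The SAP prefers the visit before the anniversary, so a late visit matters mainly when it is the only one in the window.
- Reintervention and aneurysm-related mortality are assessed through 5 years (Protocol 3.4.3), so events after the anniversary lie beyond that horizon, and 5.11 accepts telephone contact and outside records. Imaging-based patency is the outcome most exposed.
- Secondary-endpoint methods, the schedule table and some text after the window rule in 10.4.1 cannot be read. How far each 5-year outcome depends on an in-window visit cannot be confirmed.

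A reader might infer that a third to a half of subjects would lose their 5-year result, or that two thirds of those analysed would be labelled withdrawals. The documents support neither. The first needs visits spread evenly over the window and no earlier in-window visit for the subjects affected. The second turns a count of days, under one reading of 5.14, into a count of people.

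**Conclusion.** The inconsistency is real and no readable passage resolves it. On the literal text, 50% of the calendar days in the 5-year analysis window lie after the collection stop; if collection runs to one month past 5 years, the figure is 33%. The first figure treats up to 5 years as ending on the anniversary. The second borrows the month from the completion rule and takes it as 30 days.

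The number of subjects affected is unknown. They are mainly those whose only in-window imaging falls after the stop. Separately, on one reading of 5.14, subjects whose only in-window visit is more than a month from 5 years would count both as analysed and as withdrawn. The consequences are confined to 5-year secondary outcomes, chiefly imaging-based patency, and to disposition counts. The 12-month primary endpoint and its two cohort tests are not affected.

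**What to change.** 1. State one last day of data collection, equal to the end of the analysis window (5 years + 90 days), and use it in Protocol 3.2, 5.11, 5.13 and 9.1.3.
2. In Protocol 5.14, define completion by a recorded visit or contact within the same 90 days either side of 5 years.
3. Report disposition status separately from eligibility for the 5-year analysis window. A telephone contact can complete follow-up without supplying imaging for patency, so the two counts need not be equal.

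This adds no visit or scan, because it only collects what local practice already produces. It is more than an editorial change: it lengthens the stated follow-up, Protocol 6.8 requires ethics committee approval of amendments, and up to 15 sites are involved. Closure for the last subjects could be up to about 3 months later.

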5.15. Explant Procedures

The [REDACTED] may be explanted during a surgical procedure or as part of an autopsy. If this occurs during the prospective phase of the registry sites are requested to return explanted devices to the sponsor for gross and histological evaluation. Prior to planned or potential device retrieval, contact the Gore Associate managing the registry to communicate that a specimen is being retrieved from a registry subject. A specimen shipping kit will be immediately sent to the site. The specimen kit provides specific packaging and handling instructions for the specimen and contains a shipping container.

In complex aortic procedures it is expected that more than one [REDACTED] can be implanted in the same subject, if the explanted device is the only one used in the subject then the subject will be discontinued, if other [REDACTED] remain implanted the subject will continue in the registry.

6. Registry Administration

6.1. Training

CONFIDENTIAL INFORMATION

All Investigators involved in this registry must be trained on the protocol, EDC and Good Document Practice by Sponsor associates, designees, or another appropriately trained physician at the registry Site.

CONFIDENTIAL INFORMATION

MD133246 Protocol Template

Revision#: 7

Doc Type: GC

Page 17 of 37

6.2. Monitoring

Site monitoring for this protocol will be provided by [REDACTED] who are independent from the investigational site(s). Monitoring oversight will be provided by the sponsor. The Principal Investigator will be accessible to the monitor and respond to questions during monitoring visits.

The site monitors are qualified by training and experience to oversee the progress of the registry at the site and will verify that the investigators and their staff understand and adhere to both the applicable regulatory requirements and the registry protocol. In addition, they may assist in resolution of any problems that may arise during the registry.

6.3. Site Initiation

Site initiation will be performed to verify that each investigator and his / her staff understands the protocol, applicable regulations, human subject protection requirements, and the investigator's obligations. This visit will confirm that required documentation with the appropriate approval is in place prior to subject enrollment.

The registry shall not begin until the sponsor has confirmed the required approval / favorable opinion from the EC or regulatory authority have been obtained. Site Initiation can be performed remotely (web-conference) if on-site visit is not possible.

6.4. Periodic Site Monitoring

Periodic site monitoring will occur as necessary to verify continuing adequacy of facilities and adherence to the registry protocol, Good Clinical Practices (GCPs), and applicable regulations and laws that pertain to the conduct of the registry. These activities will also review the Case Report Forms (CRFs) and source documentation, the timely submission of accurate records to the sponsor, and the maintenance of proper records. A report will be written following each site visit and a follow-up letter will be provided to the site with a summary of findings. Each site will also be visited on-site or remotely contacted at close-out to confirm that all documentation is complete.

The registry will employ a risk-based monitoring approach where data are centrally reviewed for logical context, completeness, and obvious outliers. Only specific critical data variables will be source verified during on-site visits. Informed consent documentation or documentation that [REDACTED], will be reviewed for all patients to verify that all patients agreed to registry participation or are amenable for waiver. Monitoring procedures and requirements will be documented in a clinical monitoring plan developed and maintained by Gore.

6.5. Device Accountability and Storage

Due to the nature of this registry, participating sites will have utilized their commercial contractual agreement with the Sponsor or designee for device shipping, storage, use and return. Implanted device part numbers will be collected on CRFs, if available.

6.6. Core Lab

Core Lab services for this registry will be provided by [REDACTED] as referenced in Table 2.

CONFIDENTIAL INFORMATION

Table 2: Core Lab specifications

Core Lab Name	Core Lab Location	Type of Imaging Reviewed	Main Assessments	Timepoint
[REDACTED]	[REDACTED]	[REDACTED]	[REDACTED]	Pre-procedure, Post-procedure and annually

The Core Lab will perform assessments of imaging modalities according to objective process and standard procedures completed by trained and qualified personnel.

Medical imagery will be transmitted to the Core Lab using the secure, web portal functionality of the [REDACTED]. Imaging submitted through the portal will be stripped of personal health information and replaced with appropriate registry subject identifiers in automated, systemic fashion. Recipients will process received imaging according to their standard operating procedures or registry-specific processes.

[REDACTED]
Additional imaging modalities, such as magnetic resonance, may be performed during the course of the registry as part of standard practice or in response to a clinical event. Gore may request these films to be submitted to aid in the understanding of an event or to support the conduct of an independent review committee such as a Clinical Events Committee (CEC).

[REDACTED]
The site needs to upload the required imaging using [REDACTED], making sure that all PHI is redacted.

6.7. Protocol Deviations

The investigator/ sub-investigator must follow the protocol, except in the event of an immediate hazard(s) to a subject. The investigator must report those deviations and explanation immediately to the sponsor. The investigator will report the protocol deviation in accordance with the applicable regulations.

A protocol deviation is defined as any change, divergence, or departure from the registry design or procedures of a research protocol. The investigator is responsible for promptly recording and reporting protocol deviations to the sponsor and the reviewing EC per EC policy. The sponsor will determine the effect of the protocol deviation on the scientific soundness of the registry and subject safety and determine if additional reports or actions are required. Additional action may include site retraining, and / or site termination.

The investigator will not implement any changes to the protocol without first obtaining written agreement from the sponsor and documented approval from the EC, except in the event of an immediate hazard(s) to a subject. The investigator will document and report the protocol deviation in accordance with the applicable regulations. Protocol deviations will be analyzed by the sponsor and reported to regulatory authorities in accordance with applicable regulations.

CONFIDENTIAL INFORMATION

The investigator will determine the cause and implement appropriate corrective and preventive actions to address significant noncompliance to the protocol.

6.8. Protocol Amendments

The protocol may be amended by the sponsor throughout the life of the registry, as result of new findings or advisement from the applicable regulatory body or advisory committee. The investigator will obtain EC approval on all amendments in a timely manner. The sponsor will confirm proper training of Investigator and site staff on all protocol amendments.

6.9. Access to Source Data / Documents

Source data are defined as all information necessary for the reconstruction and evaluation of the clinical investigation.

The investigator and site staff should maintain adequate and accurate source documents and registry records that include all pertinent observations on each registry subject including documentation of the type and location of source documents. Source data should be attributable, legible, contemporaneous, original, accurate, and complete. Changes to source data should be traceable, should not obscure the original entry and should be explained if necessary (e.g., via an audit trail).

Where copies of the original source documents or printouts are retained, these need to be signed and dated by a member of the registry team with a statement that it is a true reproduction of the original source.

The investigator or designee will clearly mark subject clinical records to indicate the subject is enrolled in this registry.

The investigator will keep all registry records and source data, available for inspection by the sponsor, sponsor's monitors, EC, and regulatory authorities.

